7.2.2 Dose Modification for Radiotherapy

All RT treatments must begin as per planned SoC following recovery from surgery, as determined by the investigator. Ideally, this should be within 6 weeks of surgery. Treatment interruptions are to be avoided unless medically necessary. Treatment breaks must be clearly indicated in the treatment record along with the reason(s) for the treatment break(s).

Treatment breaks, if necessary, ideally should not exceed 7 treatment days at a time and 14 treatment days total. Sites should consult the PI prior to giving any RT treatment breaks. Treatment breaks should be allowed only for resolution of severe acute toxicity and/or for intercurrent illness and not for social or logistical reasons. Any treatment break(s) exceeding 2 treatment days for reasons other than toxicity/illness will be considered a protocol deviation.

Missed treatments should be compensated for with a twice a day treatment with minimum 6-hour inter-fraction interval to compensate for missed days including holidays and those for toxicity or illness once sufficiently recovered with the goal of keeping the overall treatment time confined to 6 weeks or 45 consecutive days. If BID treatments are not a part of local standard of care, RT should be continued until all 35 fractions are completed.

If cisplatin and/or pembrolizumab are discontinued, participants may stay on study treatment to complete radiation therapy.

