7.1 Treatments Administered

The study treatment(s) to be used in this trial are outlined below in [Table 2](#).

Refer to Appendix 8 for country-specific requirements.

Table 2 Study Treatment(s)

Arm Name	Arm Type	Intervention Name	Intervention Type	Dose Formulation	Unit Dose Strength(s)	Dosage Level(s)	Route of Administration	Regimen/ Treatment Period	Use	IMP/ NIMP/ AxMP	Sourcing
Arm A	Experimental	Pembrolizumab	Drug	Solution for infusion	100 mg/vial	200 mg	IV infusion	Q3W for up to 17 cycles	Test Product	IMP	Central
Arm A	Experimental	Radiotherapy	Radiation	NA (Radiation)	2 Gy/fraction	2 Gy/day	Internal radiation - systemic	Low-risk participants: 2 Gy/day in 30 fractions for a total of 60 Gy High-risk participants: 2 Gy/day in 33 fractions for a total of 66 Gy Participants with gross residual disease: 2 Gy/day in 35 fractions for a total of 70 Gy	Background treatment	NIMP/ AxMP	Local
Arm A	Experimental	Cisplatin	Drug	Solution for infusion	1 mg/mL	100 mg/m ²	IV infusion	Q3W for 3 cycles	Test Product	IMP	Local or central
Arm B	Active comparator	Radiotherapy	Radiation	NA (Radiation)	2 Gy/fraction	2 Gy/day	Internal radiation - systemic	Low-risk participants: 2 Gy/day in 30 fractions for a total of 60 Gy High-risk participants: 2 Gy/day in 33 fractions for a total of 66 Gy Participants with gross residual disease: 2 Gy/day in 35 fractions for a total of 70 Gy	Background treatment	NIMP/ AxMP	Local

Arm Name	Arm Type	Intervention Name	Intervention Type	Dose Formulation	Unit Dose Strength(s)	Dosage Level(s)	Route of Administration	Regimen/ Treatment Period	Use	IMP/ NIMP/ AxMP	Sourcing
Arm B	Active comparator	Cisplatin	Drug	Solution for infusion	1 mg/mL	100 mg/m ²	IV infusion	Q3W for 3 cycles	Test Product	IMP	Local or central

Abbreviations: AxMP=auxiliary medicinal product; EEA =European Economic Area; IMP=investigational medicinal product; IV=intravenous; NA=not applicable; NIMP=noninvestigational medicinal product; Q3W=every 3 weeks.

The classification of IMP and NIMP/AxMP in this table is based on guidance issued by the European Commission and applies to countries in the EEA. Country differences with respect to the definition/classification of IMP/NIMP/AxMP may exist. In these circumstances, local legislation is followed.

Pembrolizumab and cisplatin are allowed to be given on the same day.

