9.1.10.1.2 Radiotherapy

It is recommended that RT is started within 6 weeks after surgery. All participants in the study will be treated with 6 to 10 MV photons. The administration of standard fractionated RT regimen should follow the dose parameters in [Table 8](#). Linear accelerator or Tomotherapy based equipment is allowed. Use of intensity modulated radiation therapy (IMRT) is required, with either a sequential boost technique or Simultaneous Integrated Boost (SIB-IMRT).

Center credentialing will be performed according to criteria defined in the RT QA Manual. Participating institutions must comply with the RT QA requirements and procedures described in the RT QA manual. Sites that do not conform to the requirements of the credentialing will not be allowed to participate.

Both static and dynamic techniques IMRT techniques (including VMAT) are allowed. Dose planning, prescription, specification and reporting will be done according to International Commission on Radiation Units (ICRU) report 83 recommendations. Dose-volume constraints will be used for both dose specification and dose reporting in planning target volume (PTV) and planning organs at risk volumes (PRV)/organs at risk (OAR) (see Section 9.1.10.1.2.1). The dose-volume objectives that will be used for planning, dose specification and dose reporting in PTV, PRV and OAR are described in Section 9.1.10.1.2.1.

Table 8 Radiotherapy Dose Parameters

	Sequential Boost Plan	Simultaneous Integrated Boost (followed by additional boost if needed)
Low Risk for Microscopic Disease ^a	50 - 54 Gy in 25 - 27 fractions	54 Gy in 30 fractions
Intermediate Risk for Microscopic Disease ^b	60 Gy in 30 fractions	60 Gy in 30 fractions
Regions at High Risk ^c	66 Gy in 33 fractions	66 Gy in 33 fractions
Gross Residual Tumor ^d	70 Gy in 35 fractions	70 Gy in 35 fractions

CTV=clinical target volume; GTV=gross tumor volume; IGRT=image guided radiation therapy; PTV=planning target volume; RT=radiotherapy.

a. CTV_5000 or CTV_5400 defined as the area that is low risk for microscopic disease. This is the non-dissected neck. This RT dose is applicable for participants in the low-risk and high-risk groups.

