b. CTV_6000 defined to include the post-operative tumor bed and nodal regions at risk of microscopic spread that have not been operated on according to standard anatomic guidelines relative to location and extent of gross disease. Please note all operated sites should receive 60 Gy. This RT dose is applicable for participants in the low-risk and high-risk groups.

c. CTV_6600 defined to include 0.5 cm expansion on regions thought to be at high risk of recurrence (eg, areas of extranodal extension or positive margins of resection). This RT dose is applicable for participants in the high-risk group.

d. For participants who do not undergo planned curative surgery or for incomplete resection with gross residual tumor: primary surgical tumor bed encompassing preoperative GTVs plus up to 0.5 cm to define CTV_7000.

All PTVs defined as 0.3 to 0.5 cm expansions on CTVs based on method and frequency of IGRT.

Radiotherapy treatment for participants that undergo surgery will be delivered over 6 to 6.5 weeks, depending on risk of recurrence, by incorporating 5 fractions per week (example: 5 fractions over 5 days (1 fraction per day), 2 days off).

Participants that do not undergo surgery as planned, for whatever reason, and proceed directly to salvage CRT may receive a RT dose of 70 Gy (total of 35 fractions) over 6.5 to 7 weeks.

When Sequential Boost IMRT is used, planning and delivery should be as follows: 50 Gy in 25 fractions or 54 Gy delivered in 27 fractions of 2 Gy/fraction, followed by a boost of 6 Gy in 3 additional fractions of 2 Gy/fraction. If an additional boost is required for high risk area such as areas of extranodal extension and/or positive margins, an additional 6 Gy can be delivered in 2 Gy/fraction in 3 fractions.

If SIB-IMRT is used, potential planning and delivery can be as follows: 60 Gy delivered in 30 fractions of 2 Gy/fraction given simultaneously with 54 Gy in 1.8 Gy/fraction. If an additional boost is required for high risk area such as areas of extranodal extension and/or positive margins, an additional 6 Gy can be delivered in 2 Gy/fraction for 3 fractions.

If all of the surgical area is considered at high risk for disease recurrence, another potential prescription option can be 66 Gy fractions given in 33 fractions at 2 Gy/fraction.

If gross disease is identified, in the case of a participant with incomplete resection, an additional boost up to 70 Gy may be delivered to the gross disease area.

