All participants must have routine imaging performed to verify treatment set up. The minimum imaging requirement is once weekly orthogonal KV images commencing on the first day of treatment and reviewed by the managing radiation oncologist. Centers are strongly encouraged to employ daily volumetric image guidance with either accelerator mounted KV or MV cone beam CT or tomotherapy CT images utilizing matching of bony anatomy. The margin for PTV can be reduced to 3 mm if daily IGRT is performed.

Table 11 details radiotherapy compliance criteria.

Table 11 Radiotherapy Compliance Criteria

	Per Protocol	Variation Acceptable	Deviation Unacceptable
Prescription Dose	Delivered daily or total dose to any PTV is within 5% of the protocol dose.	Delivered daily or total dose to any PTV differs from the protocol specified dose by 6-10%	Delivered daily or total dose to any PTV differs from the protocol specified dose by >10%
Dose Uniformity	Dose to 95% of any PTV is > 95% of prescribed dose.	Dose to 95% of any PTV <95% of the prescribed dose; >10% of the highest dose PTV >110% of prescribed dose	Dose to 95% of any PTV <90% of the prescribed dose; >10% of the highest dose PTV >120% of prescribed dose
Volume	Volumes follow protocol guidelines	PTV margins are less than the protocol specified margins or excessively large	CTV does not encompass areas at risk.
Organs at Risk			Dose to 2% of PRV spinal cord >50 Gy Dose to 2% of PRV brainstem >54 Gy
Interruptions		Uncompensated Interruptions more than 2 days for reasons other than toxicity	Uncompensated Interruptions more than 10 days for reasons other than toxicity
Abbreviations: CTV = clinical target volume; PRV = Planning Organ at Risk Volume; PTV = planning target volume.			

9.1.10.1.2.3 Supportive Care for Head and Neck Radiotherapy

Radiation-induced head and neck toxicity is well known and has been well described. It is expected to vary according to the total dose and the concomitant use of chemotherapy. Locoregional toxicity will be monitored during treatment using CTCAE v. 4.0 and will be reported in the database. Supportive care will be provided according to local SoC.

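### Section 7.2.2 tells sites to finish interrupted radiotherapy at 35 fractions whatever the risk group (literally 70 Gy, not 60 Gy, at low risk), and the 50 Gy sequential-boost start totals 56 or 62 Gy, not 60 or 66 Gy

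*Combined protocol and SAP*

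**What the plan says.** Section 7.2.2 covers interruptions of radiotherapy in both arms. Missed treatments are to be made up twice daily, aiming at an overall time of 6 weeks or 45 days. For sites where that is not usual practice it adds: "If BID treatments are not a part of local standard of care, RT should be continued until all 35 fractions are completed". The sentence is not limited to any risk group.

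The prescription elsewhere depends on risk. Table 2 in Section 7.1 gives "Low-risk participants: 2 Gy/day in 30 fractions for a total of 60 Gy", then 33 fractions (66 Gy) for high-risk participants and 35 fractions (70 Gy) for gross residual disease. The schedule of activities and Table 8 agree. Section 9.1.10.1.2 attaches 35 fractions to participants who miss planned surgery and "proceed directly to salvage CRT may receive a RT dose of 70 Gy (total of 35 fractions").

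The same section describes the sequential-boost technique: "50 Gy in 25 fractions or 54 Gy delivered in 27 fractions of 2 Gy/fraction, followed by a boost of 6 Gy in 3" further fractions, with another 6 Gy in 3 fractions where high-risk areas need it. For the intermediate-risk volume Table 8 requires "60 Gy in 30 fractions", and for high-risk regions 66 Gy in 33. Footnote b of Table 8 adds: "Please note all operated sites should receive 60 Gy". Table 10 sets the median dose for these two volumes at 60 Gy and 66 Gy, each within 2%.

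**The concern.** Both passages are instructions that a site acts on, and each contradicts the protocol's own dose tables. Section 7.2.2 gives everyone with missed days and no twice-daily make-up the fraction count that belongs to gross residual or unresected disease. The boost paragraph offers two starting doses but one boost size, so at most one of the two can reach the required total.

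What is at stake is the dose a participant receives. Radiotherapy is given in both arms under the same wording, so this is a question of participant safety and of having a clear standard for dose compliance. It is not a claim about bias or power.

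The two errors differ in how exposed they are. Plans go to the RT vendor for approval before radiotherapy starts. A 56 Gy plan would probably be stopped there because it misses the Table 10 objective. The 35-fraction rule takes effect only after a break in treatment, when that approval has already been given.

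**Working it through.** **Inputs.** 2 Gy per fraction and 30, 33 or 35 fractions by risk group (Table 2, Table 8); 35 fractions after a break without twice-daily make-up (Section 7.2.2); sequential start of 50 Gy in 25 or 54 Gy in 27, first boost 6 Gy in 3, optional further 6 Gy in 3 (Section 9.1.10.1.2); median dose within 2% (Table 10); dose compliance bands of 5%, 6-10% and more than 10% (Table 11); overdose at 20% or more above prescription (Section 9.4).

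**The plan's own totals.** Total dose = fractions × 2 Gy.
- 30 × 2 = 60 Gy; 33 × 2 = 66 Gy; 35 × 2 = 70 Gy. Tables 2 and 8 are reproduced.

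**35-fraction rule.** Excess = 70 / prescribed dose - 1.

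| Group | Prescribed | Literal 7.2.2 | Excess | Table 11 band |
|---|---|---|---|---|
| Low risk | 60 Gy in 30 | 70 Gy in 35 | +10 Gy, +16.7% | unacceptable deviation (over 10%) |
| High risk | 66 Gy in 33 | 70 Gy in 35 | +4 Gy, +6.1% | acceptable variation (6-10%) |
| Gross residual or unresected | 70 Gy in 35 | 70 Gy in 35 | 0 | per protocol |

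The bands are worded "Delivered daily or total dose to any PTV differs from the protocol specified dose by >10"% and "Delivered daily or total dose to any PTV differs from the protocol specified dose by 6-10"%. The overdose threshold for a 60 Gy prescription is 1.2 × 60 = 72 Gy, so 70 Gy would not be reported as an overdose.

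**Time goal in the same paragraph.** At 5 fractions a week, 30 fractions take 30/5 = 6 weeks and 35 take 35/5 = 7 weeks. Assuming a Monday start and no interruption, 30 fractions end on day 5 × 7 + 5 = 40, 33 on day 6 × 7 + 3 = 45, and 35 on day 6 × 7 + 5 = 47. The 45-day goal fits 30 and 33 fractions but not 35.

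**Sequential boost.** Total = start + 6 Gy, then + 6 Gy for high-risk areas.

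| Start | After first boost | Against 60 Gy | After second boost | Against 66 Gy |
|---|---|---|---|---|
| 54 Gy in 27 | 60 Gy in 30 | 0 | 66 Gy in 33 | 0 |
| 50 Gy in 25 | 56 Gy in 28 | -6.7% | 62 Gy in 31 | -6.1% |

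Table 10 limits: 60 Gy ± 2% is 58.8 to 61.2 Gy, so 56 Gy is 58.8 - 56 = 2.8 Gy too low. 66 Gy ± 2% is 64.68 to 67.32 Gy, so 62 Gy is 64.68 - 62 = 2.68 Gy too low. Both shortfalls fall in the 6-10% band of Table 11.

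**Corrected 50 Gy branch.** The first boost must be 60 - 50 = 10 Gy, that is 5 fractions. Then 50 + 10 = 60 Gy in 30 fractions, and 60 + 6 = 66 Gy in 33.

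**The case against.** The best reply is that nobody would read Section 7.2.2 this way. The risk-specific doses appear in the schedule of activities, Table 2 and Table 8, and the sentence can be taken simply as telling sites not to cut a course short. The 45-day goal just before it does not fit 35 fractions, which suggests a stray number and not a second prescription. This is a fair account of what was probably intended, but nothing in the protocol withdraws the figure.

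A second point is that Table 11 measures delivered dose against the dose the protocol specifies. If Section 7.2.2 really specified 70 Gy, giving it would be no deviation; if 60 Gy stands, Table 11 would expose the excess. That is logically correct, but it shows the difficulty: a site obeying one section breaches the dose set by another, and Table 11 would reveal this only after delivery.

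Third, there are safeguards. Section 7.2.2 asks sites to consult the PI before any break, and five extra fractions would exceed the approved plan and the Table 10 objectives. The RT QA Manual, which is not among the documents, may require re-approval of added fractions. So it cannot be said that nothing would catch the error, only that the pre-treatment approval comes too early to do so.

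Finally, the reach is narrow: missed days, a site without twice-daily make-up, and a literal reading. Section 10.1 states that 714 participants have been enrolled, so few radiotherapy starts may remain. The 50 Gy shortfall is the smaller problem, likely to be caught at plan review. These points limit the practical consequence; they do not make either instruction correct.

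**Conclusion.** The concern holds: both instructions are wrong as written and should be fixed. The larger error is the low-risk case under Section 7.2.2, the only one of the four discrepancies to exceed 10%. The high-risk case and the two totals from the 50 Gy start are each off by 6-7%, outside the 5% per-protocol band but within the range Table 11 tolerates.

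The 35-fraction result rests on a literal reading of that sentence. The boost result needs no interpretation, but applies only to the 50 Gy start. How many participants were affected, if any, cannot be derived from the documents. No estimate, test or power figure changes.

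**What to change.** - **Section 7.2.2:** replace the fixed count with all prescribed fractions, stated as 30, 33 or 35 according to risk group.
- **Section 9.1.10.1.2, sequential boost:** give the 50 Gy start its own first boost so that operated sites reach 60 Gy in 30 fractions, for example 10 Gy in 5, followed by 6 Gy in 3 where 66 Gy is needed. Leave the 54 Gy branch alone.
- **Confirmation and issue:** have the sponsor's radiation-oncology lead confirm both changes, then send them as a clarification to sites and the RT QA vendor.
- **Participants already treated:** among those with radiotherapy breaks and no twice-daily make-up, compare delivered with prescribed fractions. Section 7.2.2 already requires breaks and their reasons to be recorded.

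The cost is two sentences and a review of radiotherapy records already held for compliance purposes. Sample size, analysis and data collection do not change.

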7.2.3 Dose Modification for Cisplatin

Participants can have 2 levels of dose reductions of cisplatin throughout the course of the study for toxicities as described in [Table 5](#).

If further toxicity occurs or the criteria for resuming treatment are not met, the participant must be discontinued from that drug and continue to participate in the study. If a participant experiences several toxicities and there are conflicting recommendations, follow the most conservative dose adjustment recommended (dose reduction appropriate to the most severe toxicity).

If pembrolizumab is discontinued, the participants may continue with cisplatin and radiation therapy.

Table 5 Dose Levels for Cisplatin

	Dose Level 0	Dose Level -1	Dose Level -2	Dose Level -3
Cisplatin	100 mg/m ²	80 mg/m ²	60 mg/m ²	Discontinue

7.2.3.1 Cisplatin-Related Toxicity

The major dose-limiting toxicities observed with single-agent cisplatin are the following:

- Gastrointestinal toxicity: nausea and vomiting.
- Nephrotoxicity: renal function impairment associated with tubular damage and manifested with elevation in serum creatinine and urea and decrease in CrCl. It is also associated with serum electrolyte disturbances, like hypomagnesemia, hypocalcemia, hyponatremia, hypokalemia and hypophosphatemia.
- Ototoxicity: cumulative and not reversible damage, manifesting with hearing loss in the high frequency.
- Hemotoxicity: neutropenia, thrombocytopenia, anemia.
- Neurotoxicity: manifesting with peripheral neuropathy and paresthesia in both upper and lower extremities.

7.2.3.2 Dose Modification for Cisplatin

For every treatment infusion, a full dose of cisplatin will be given if neutrophils are $\geq 1.0 \times 10^9/L$ and platelets $\geq 75 \times 10^9/L$. If these levels are not reached, blood counts should be performed at the investigator's judgment but it is recommended at least weekly to document recovery. Once a participant has recovered, cisplatin should be administered (without waiting for the next cycle). If hematological toxicity has not resolved, the participant should not receive further cisplatin. The participant can continue with RT with or without pembrolizumab (depending on assigned treatment arm), and will be followed-up according to study protocol. Cisplatin may be administered up to 1 week following completion of RT.

The following dose reductions of cisplatin should be applied and should be carried over through all subsequent infusions (ie, no dose escalation). In the event that cisplatin treatment is stopped, no substitution with, for example, carboplatin, will be allowed. Cessation of cisplatin therapy is not, in itself, a reason for discontinuing the participant from the study.

Dose Reduction for Neutropenia

In the case of treatment delay due to delayed neutrophil recovery, the following policies are recommended:

- If neutrophil count has resolved to $\geq 1.0 \times 10^9/L$ in ≤ 1 week, administer the full dose of cisplatin.
- If neutrophil count has resolved to $\geq 1.0 \times 10^9/L$ in > 1 week but ≤ 2 weeks, proceed with a dose reduction of cisplatin.

Dose Reductions for Febrile Neutropenia

In case of any febrile neutropenia (at least CTCAE 4.0 Grade 3: absolute neutrophil count $<1000/\text{mm}^3$ with a single temperature of $>38.3^\circ\text{C}$ (101°F) or a sustained temperature of $\geq 38^\circ\text{C}$ (100.4°F) for more than 1 hour), it is recommended that the participant is hospitalized and treated with antibiotics as appropriate. After a period of febrile neutropenia, additional precautions have to be taken for the subsequent infusions and the cisplatin dose should be reduced.

Dose Reductions for Thrombocytopenia

If complicated thrombocytopenia \geq Grade 3, with hemorrhage and/or requiring prophylactic/therapeutic platelet transfusions (recommended at $<10 \times 10^9/\text{L}$, but dependent upon local transfusion policy) occurs at any point during the treatment, appropriate supportive care should be given and cisplatin treatment should be delayed until platelets are $\geq 75 \times 10^9/\text{L}$.

In any case at the occurrence of Grade 4 thrombocytopenia at nadir ($<25 \times 10^9/\text{L}$), cisplatin dose reduction should take place in the subsequent infusion.

Dose Reduction for Renal Toxicity

In case of renal toxicity, the cisplatin dose must be reduced as in [Table 6](#):

Table 6 Cisplatin Dose Reduction for Renal Toxicity

Creatinine Clearance	Cisplatin
$\geq 60 \text{ mL/min}$	100 mg/m^2
50-59 mL/min	80 mg/m^2
40-49 mL/min	60 mg/m^2
$<40 \text{ mL/min}$	Discontinue

Dose Reduction for Peripheral Neuropathy

A neurological examination should be performed at screening, before the second cisplatin injection per local regulations by the investigator or qualified designee. In case of symptoms or signs experienced by the participant, more frequent examinations should be performed per local regulations by the investigator or qualified designee and the following dose modifications are required:

Grade 0, 1 (CTCAE v.4.0): No change.

Grade 2 (CTCAE v.4.0): Cisplatin will be reduced to 60 mg/m^2 .

Grade ≥ 3 (CTCAE v.4.0): Cisplatin will be discontinued.

Dose Reduction for Ototoxicity

Cisplatin is known to cause high frequency hearing loss. Follow local product label and institutional guidelines (eg, for France see Appendix 7 for the most recent version of the medicines SmPC). The following dose modifications are required:

- If Grade 1 or 2 hearing loss (CTCAE v.4.0) occurs, the risk of additional hearing loss versus the potential benefit of continuing cisplatin chemotherapy should be made.
- Grade 3 and 4 hearing loss (CTCAE v.4.0) is an indication to discontinue cisplatin.

Dose Modification for Other Toxicities

If toxicity has not resolved the participant should not receive further cisplatin. The participant will continue with RT and will be followed-up according to the study protocol. Cisplatin can be administered up to 1 week following completion of RT.

Please also refer to the Multinational Association of Supportive Care in Cancer and European Society for Medical Oncology guidelines for treatment and prevention of emesis caused by highly emetic compounds [Roila, F., et al 2016]. Dose Modification for Cisplatin for other toxicities are presented in [Table 7](#).

Table 7 Dose Modification for Cisplatin – Other Toxicities

Category	Toxicity	Hold Cisplatin Treatment for Grade	Timing for Restarting Cisplatin Treatment	Dose Level for Restarting Cisplatin Treatment	Discontinue Platinum
Non-hematologic	Creatinine clearance Decreased	Please see Table 6 for guidance on dose level reduction and discontinuation.			
	All other non-hematologic toxicities ^b	3-4 ^a	Toxicity resolves to Grade 0-1	Reduce by 1 dose level	Toxicity does not resolve or if >2 Dose Level reductions exceeded
	Laboratory adverse event ^b	4	Toxicity resolves to Grade 2 or less	Reduce by 1 dose level	Toxicity does not resolve or if >2 Dose Level reductions exceeded

^a Permanent discontinuation should be considered for any severe or life-threatening event. Consult Sponsor before restarting treatment after Grade 4 drug-related AE

^b Participants with intolerable or persistent Grade 2 drug-related AEs may hold at physician discretion. Permanently discontinue from cisplatin for persistent Grade 2 adverse reactions for which treatment has been held, and did not recover to Grade 0-1 of the last dose. With investigator and Sponsor agreement, participants with a laboratory AE still at Grade 2 may continue in the study only if asymptomatic and controlled.

